8.4 Interim Safety Analysis

We have generated stopping rules based on the three year historical data from the JTCC for 5 criteria: NRM, Relapse, Graft Failure or Delay, Drug Intolerance, and Grade III-IV GVHD. These rules and the operating characteristics for the algorithms are presented below.

Stopping rules

In this section, the stopping rules for each of the adverse events non-relapse mortality, relapse, graft failure, intolerance to Telmisartan and Grade 3 or 4 GVHD by day 100 are described. Each of the 5 toxicities is monitored at 1% Type I error, i.e., the probability of stopping by chance the trial when in fact the toxicity rate observed in historical data is true. Thus, the repeated significance test maintains the level of the toxicity through all the monitoring points to be 1%.

Further, jointly all 5 toxicities have probability $(1-(1-0.01)^5)=0.049$ probability of stopping the trial by chance when the null hypotheses are true.

Non-Relapse Mortality (NRM) at 100 days

If the non-relapse mortality in patients receiving Telmisartan the rate of NRM exceeds 22% then the study will be stopped. The operating characteristics of the stopping rule are described below. Based on historical data from the cancer center registry, it was assumed that 15% incidence of NRM was considered expected and incidence greater than 22% would be considered unacceptable.

Using repeated significance testing (Jennison and Turnbull) with 15.0% as lower proportion and 22.0% as higher proportion, 1% alpha level, and 80% power for early termination, shape parameter of the boundary, $\delta=0.2$, with priority on alternative hypothesis and continuous monitoring, the following stopping guidelines were computed by the *toxbdry* function in the Clinfun package in R 3.2.0.

Table 5. Stopping Boundaries for NRM at 100 days using continuous monitoring

Monitoring Look	Number of Patients at Monitoring Look	Stop if Number of Toxicities is at least
1	2	2
2	7	3
3	12	4
4	18	5
5	24	6
6	29	7
7	35	8
8	41	9
9	47	10
10	54	11
11	60	12

The trial will be terminated if 2 patients out of the first 2 patients receiving experimental drug, Telmisartan, experience NRM by day 100. If out of the first 7 patients, 3 or more have NRM by day 100 then trial will be stopped. The boundaries were obtained such the Type I error, fixed at 1%, was spent over the multiple looks, hence the probability of stopping the trial prematurely by chance is 0.01.

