For this continuous monitoring scheme, the trial will be terminated if 2 or more patients out of the first 3 patients receiving experimental drug, Telmisartan, experience relapse by day 100. If out of the first 8 patients, 3 or more have relapse by day 100 then trial will be stopped, and so forth. Out of all the 15 patients that receive Telmisartan, if 4 or more patients have relapse by day 100 then the drug will be considered more toxic than standard treatment. The boundaries were obtained such the Type I error, fixed at 1%, was spent over the multiple looks, hence the probability of stopping the trial prematurely by chance is 0.01.

Table 8. Operating characteristics for the stopping boundaries for Relapse by Day 100

Probability Of Toxicity	Probability of crossing low bndry	Probability of stopping low bndry	Expected sample size low bndry	Probability of crossing high bndry	Probability of stopping high bndry	Expected sample size high bndry
0.120	0.312	0.312	48.4	0.307	0.307	48.8
0.134	0.418	0.418	44.8	0.414	0.414	45.2
0.148	0.527	0.527	40.8	0.523	0.523	41.3
0.162	0.631	0.631	36.9	0.628	0.628	37.3
0.176	0.724	0.724	33.0	0.721	0.721	33.4
0.19	0.801	0.801	29.4	0.799	0.799	29.8

Bndry, boundary.

From the operating characteristics, the probability of stopping the trial due to grade 3 or 4 GVHD if the level of toxicity is at high level of 36% is 0.79. The expected sample size at termination of the trial is 31.8, if Telmisartan in fact more toxic than standard treatment.

Graft Failure at Day 100 (includes delayed engraftment and failure)

If the incidence of graft failure by day 100 in patients receiving Telmisartan exceeds 7.0% then the study will be stopped. The operating characteristics of the stopping rule are described below. Based on historical data from the cancer center registry, it was assumed that 7.0% incidence of relapse was considered expected and incidence greater than 12.0% would be considered unacceptable.

Using repeated significance testing (Jennison and Turnbull) with 7.0% as lower proportion and 12.0% as higher proportion, 1% alpha level, and 80% power to for early termination, shape parameter of the boundary, $\delta=0.2$, giving priority to the alternative hypothesis, and continuous monitoring the following stopping guidelines were computed by the *toxbdry* function in the Clinfun package in R 3.2.0.

Table 9. Stopping Boundaries for Graft Failure at Day 100

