Monitoring Look	Number of Patients at Monitoring Look	Stop if Number of Toxicities is at least
1	9	2
2	21	3
3	33	4
4	45	5
5	58	6
6	60	7

The trial will be terminated if 2 or more patients out of the first 9 patients receiving experimental drug, Telmisartan, experience graft failure by day 100. If out of the first 21 patients, 3 or more have graft failure by day 100 then trial will be stopped. The boundaries were obtained such the Type I error, fixed at 1%, was spent over the multiple looks, hence the probability of stopping the trial prematurely by chance is 0.01.

Table 10. Operating characteristics for the stopping boundaries for Graft Failure Day 100

Probability Of Toxicity	Probability of crossing low bndry	Probability of stopping low bndry	Expected sample size low bndry	Probability of crossing high bndry	Probability of stopping high bndry	Expected sample size high bndry
0.07	0.373	0.373	46.1	0.365	0.365	46.2
0.08	0.477	0.477	42.4	0.467	0.466	42.5
0.09	0.576	0.576	38.7	0.565	0.565	38.8
0.10	0.666	0.666	35.0	0.655	0.654	35.1
0.11	0.744	0.744	31.6	0.734	0.733	31.7
0.12	0.809	0.809	28.5	0.799	0.798	28.6

Bndry, boundary.

From the operating characteristics, the probability of stopping the trial due to graft failure if the level of toxicity is at high level of 12% is 0.798. The expected sample size at termination of the trial is 28.6, if Telmisartan in fact more toxic than standard treatment.

Telmisartan Intolerance (includes angioedema and grade 3 or greater drug related adverse events after dose adjustments)

We use 5% as our acceptable rate of intolerance for drug treatment. Using repeated significance testing (Jennison and Turnbull) with 5.0% as lower proportion and 11.0% as higher proportion, 1% alpha level, and 80% power to for early termination, shape parameter of the boundary, delta=0.2, giving priority to the alternative hypothesis and continuous monitoring, the following stopping guidelines were computed by the *toxbdry* function in the Clinfun package in R 3.2.0.

Table 11. Stopping Boundaries for Intolerance to Telmisartan at Day 100

Monitoring Look	Number of Patients at Monitoring Look	Stop if Number of Toxicities is at least
1	8	2
2	22	3
3	38	4
4	55	5
5	60	6

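### Section 8.4 states a 1% false-stop rate per safety rule, but its own tables give 22–37%; the graft-failure trigger equals the expected rate, and the GVHD and relapse text is mislabelled

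*Combined protocol and SAP*

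**What the plan says.** Section 8.4 sets five stopping rules, each with a boundary table (Tables 5, 7, 9, 11, 13) and a table of operating characteristics (Tables 6, 8, 10, 12, 14).

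- **Error rates.** The opening text says "Each of the 5 toxicities is monitored at 1% Type I error" and defines this as the chance of stopping when the historical rate is true. It then gives 0.049 as the joint "probability of stopping the trial by chance when the null hypotheses are true". Under every boundary table it repeats "hence the probability of stopping the trial prematurely by chance is 0.01". The NRM rule is said to have "1% alpha level, and 80% power for early termination", and the other four are described in the same terms.
- **Graft failure.** The trigger sentence reads "If the incidence of graft failure by day 100 in patients receiving Telmisartan exceeds 7.0% then the study will be stopped". The same paragraph says "it was assumed that 7.0% incidence of relapse was considered expected and incidence greater than 12.0% would be considered unacceptable". The text under Table 9 says the trial is "terminated if 2 or more patients out of the first 9 patients receiving experimental drug, Telmisartan, experience graft failure by day 100". The parallel NRM sentence uses the unacceptable rate ("the rate of NRM exceeds 22% then the study will be stopped"), as do those for relapse (19%) and GVHD (36%).
- **Grade 3 or 4 GVHD.** The trigger sentence, the sentence giving 26% and 36%, the sentence about 4 of the first 5 patients, and the titles of Tables 13 and 14 all name NRM.
- **Relapse.** The summary under Table 8 reports grade 3 or 4 GVHD, 36%, 0.79 and 31.8.

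**The concern.** A DSMB needs one rule per event and a true statement of how often that rule stops the trial by chance. Section 8.4 falls short on both.

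The false-stop rate is the main problem. The prose says 1 in 100 per event, while the tables say roughly 1 in 5 to 1 in 3. A board relying on the prose would treat a crossing as strong evidence of harm when the boundary is often crossed at the expected rate.

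The graft-failure sentence and Table 9 give different stopping counts, and nothing states which one governs. Read literally, the GVHD subsection gives NRM a second boundary and a second expected rate (26% as well as 15%), and no boundary table is named for grade III–IV GVHD. The relapse summary misreports that rule's operating characteristics.

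**Working it through.** **1. Reproducing the tables.** Inputs are the printed boundaries and the expected and unacceptable rates in Section 8.4. Let f(n,k) be the probability of k events after n patients with no earlier crossing. Then f(n,k) = f(n−1,k)(1−p) + f(n−1,k−1)p. Any mass at or above the boundary is removed and counted as a crossing, patient by patient to n = 60.

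| Rule | Expected / unacceptable rate | Stated type I error | Printed crossing at expected rate (low / high boundary) | Recomputed at expected rate | Recomputed at unacceptable rate | Recomputed expected n at unacceptable rate |
|---|---|---|---|---|---|---|
| NRM | 15% / 22% | 0.01 | 0.343 / 0.340 | 0.341 | 0.798 | 29.7 |
| Relapse | 12% / 19% | 0.01 | 0.312 / 0.307 | 0.307 | 0.799 | 29.8 |
| Graft failure | 7% / 12% | 0.01 | 0.373 / 0.365 | 0.365 | 0.799 | 28.6 |
| Intolerance | 5% / 11% | 0.01 | 0.222 / 0.219 | 0.219 | 0.798 | 30.6 |
| Grade III–IV GVHD | 26% / 36% | 0.01 | 0.253 / 0.247 | 0.247 | 0.790 | 31.8 |

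The high-boundary columns are reproduced to about 0.001; the 1% is not. Testing only at the listed looks leaves the crossing probabilities unchanged.

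**2. A check by hand.** The first look alone already exceeds 1%:

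- NRM, 2 of 2: 0.15² = 0.0225.
- GVHD, 3 of 3: 0.26³ = 0.0176.
- Graft failure, at least 2 of 9: 1 − 0.93⁹ − 9(0.07)(0.93⁸) = 0.127.
- Relapse and intolerance, by the same binomial tail: 0.040 and 0.057.

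**3. Joint probability.** The plan computes 1 − 0.99⁵ = 0.049. Its own tabulated high-boundary values in the same formula give 1 − (0.660 × 0.693 × 0.635 × 0.781 × 0.753) = 0.829. Without independence, the joint value is at least the largest single one, 0.365.

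**4. Can 1% and 80% both hold?** Any stopping rule using at most 60 patients is a test on those 60 outcomes. By Neyman–Pearson, its power at size 1% cannot exceed that of the randomised most powerful test at n = 60. The bounds are 0.195 (NRM), 0.235 (relapse), 0.190 (graft failure), 0.340 (intolerance) and 0.270 (GVHD).

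**5. Graft-failure trigger.** More than 7% of 60 is more than 4.2, so 5 events; Table 9 requires 7 at n = 60. The full comparison at n = 60 is:

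| Rule | Count from percentage sentence | Count from table |
|---|---|---|
| NRM | 14 | 12 |
| Relapse | 12 | 11 |
| Grade III–IV GVHD | 22 | 21 |
| Graft failure | 5 | 7 |

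No sentence matches its table, and at n = 60 graft failure is the only one whose sentence is the stricter. Its effect depends on when it is applied. At a true rate of 7%:

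| Schedule | Sentence at 7% | Same sentence at 12% | Table 9 |
|---|---|---|---|
| Only at n = 60 | 0.412 | 0.057 | – |
| At Table 9's looks (9, 21, 33, 45, 58, 60) | 0.698 | 0.310 | 0.365 |
| After every patient | 0.807 | 0.557 | 0.365 |

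At Table 9's looks the 7% sentence stops at 1, 2, 3, 4, 5, 5 events; the table stops at 2, 3, 4, 5, 6, 7.

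**6. Labels.** Table 13 belongs to GVHD: it sits under that heading, GVHD is among the five listed criteria, and Section 8.3.1 gives 46/178 = 26% for grade III–IV GVHD. If Table 13 were also applied to NRM, Table 5's count is never above Table 13's at any n. Using both at a true 22% NRM gives 0.798, the same as Table 5 alone.

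**7. Copied and misprinted figures.** The summary under Table 8 gives 36%, 0.79 and 31.8; Table 8 gives 19%, 0.799 and 29.8. In Table 14 at 0.32, the low-boundary stopping probability (0.695) exceeds its crossing probability (0.597), which is impossible. The high-boundary expected size in that row is 35.2. The printed boundary recomputes to 0.585 and 40.2.

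**The case against.** The best defence is that the correct probabilities are printed next to the wrong ones. Each subsection except intolerance's pairs a percentage sentence with a count table and a worked count sentence, and only the counts come with looks. A DSMB would naturally use Table 9, so the 7.0% looks like a drafting slip. The plan also discloses that the boundaries give priority to the alternative hypothesis, which probably explains why about 80% power was kept and 1% was not. The error leads to too much stopping, not to missed harm.

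Most of this is fair but leaves the main point intact. The count tables are the more workable rules, yet the plan never says so, and no percentage sentence agrees with its table at n = 60. Giving priority to the alternative explains the tables but does not make the 1% true, and the prose asserts 0.01 under all five.

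Four limits do stand:

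- The graft-failure probabilities depend on an unstated schedule (0.41 to 0.81).
- The statement that graft failure's sentence is the strict one holds only at n = 60. Applied after every patient, the 22% NRM sentence would stop at 1 death among 4 patients, where Table 5 needs 3. Table 9's count of 7 applies only at patients 59 and 60.
- The joint 0.829 assumes independence of events that are linked or competing.
- The NRM labels and the copied relapse summary are editorial and change no stopping decision.

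**Conclusion.** The concern holds. The stated 1% per rule is wrong for the printed boundaries: the false-stop probability is 0.219 to 0.365 (high boundary; 0.222 to 0.373 on the low boundary). The stated joint 0.049 becomes 0.829 under the plan's own independence assumption and is at least 0.365 under any dependence. These results assume independent patients at the stated expected rates and monitoring to 60. Detection at the unacceptable rates, about 0.79 to 0.80, is as tabulated, but it cannot coexist with 1% at this sample size.

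The graft-failure trigger sentence conflicts with the rest of its subsection (5 against 7 events at n = 60). The remaining slips are labels and copied figures. The section should be corrected so that the DSMB does not work from the 1% claim.

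**What to change.** 1. Replace the 1% and 0.049 statements, including the repeats under each boundary table, with the tabulated false-stop probabilities, once the sponsor confirms that those boundaries are intended. If 1% was intended, the 80% power claim cannot stand with 60 patients, and the boundaries and their power must be recomputed and restated. That choice belongs to the sponsor and the DSMB.
2. State whether the count tables or the percentage sentences are operative, and on what schedule.
3. Reconcile the graft-failure trigger sentence with the 7%/12% design, Table 9 and the count sentence beneath it. Correct the reference to relapse in that paragraph to graft failure.
4. In the grade 3 or 4 GVHD subsection, relabel the three sentences and the titles of Tables 13 and 14 as grade III–IV GVHD.
5. Replace the summary under Table 8 with that table's own values (relapse, 19%, 0.799, 29.8), and recheck the 0.32 row of Table 14.

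The cost is a wording amendment circulated to the DSMB, with no new data or patients. Recalculation is needed only if the sponsor says the tabulated boundaries were not intended.

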9.0 Safety Monitoring

9.1 Adverse Events

For the purposes of this research study, an “adverse event” (AE) is any untoward medical occurrence associated with the use of a study drug, whether or not considered drug related. An AE can be a clinical event in the form of signs, symptoms, disease, or laboratory or physiological observations occurring in a study participant, regardless of causal relationship. A “pre-existing” condition is one that is present prior to study drug administration and is reported as part of the patient’s medical history. A pre-existing condition should be reported as an AE only if the frequency, intensity, or character of the pre-existing condition worsens during the course of the study.

Laboratory abnormalities associated with subjects underlying disease or related to the subject’s HCT will not be considered adverse events. However, a laboratory abnormality (e.g. a clinically significant change detected on clinical chemistry or hematology) that is independent from the underlying medical condition and/or HCT that requires medical or surgical intervention, or leads to study drug discontinuation, will be considered an AE.

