5.4.2 Agents That Increase the Risk of Renal Failure

Hyperkalemia may occur in patients on telmisartan, particularly in patients with advanced renal impairment, heart failure, on renal replacement therapy, or on potassium supplements, potassium-sparing diuretics, potassium-containing salt substitutes or other drugs that increase potassium levels. Potassium-sparing diuretics such as spironolactone, and angiotensin-

converting-enzyme (ACE) inhibitors will be discontinued prior to start of study and will not be used in conjunction with telmisartan during the study unless deemed necessary by the HCT clinical physicians, due to potential interactions leading to renal toxicity. Potassium supplements will also be discontinued, and re-started gradually if need is indicated by electrolyte monitoring. Foods high in potassium will be limited to safe levels during the period of telmisartan administration except as specifically allowed by the physician monitoring the patient's electrolyte status.

In patients who are elderly, volume-depleted (including those on diuretic therapy), or with compromised renal function, co-administration of NSAIDs, including selective COX-2 inhibitors, with telmisartan, may result in deterioration of renal function, including possible acute renal failure. These effects are usually reversible. Caution will be taken when administering NSAIDs to study subjects, and renal functions will be monitored.

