7.2 Safety Endpoints

7.2.1 Exams and laboratory assessments

Physical exam, vital signs, CBC, and Chemistry panels reflect the standard of care for patients undergoing HCT. Exams and tests will be performed according to John Theurer Cancer Center SOPs. Any deviations from baseline measurements will be noted and assessed for severity and causality. Hematologic abnormalities determined to be related to the subject's disease or HCT will not be recorded as adverse events.

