9.2 Recording Adverse Events

All AE’s will be graded according to the NCI’s Common Terminology Criteria for Adverse Events (CTCAE) version 4.03. All grade 3, 4, and 5 non-hematologic adverse events will be recorded. Grade 1 and 2 adverse events will be recorded if they are: 1) potentially associated with GvHD, or 2) potentially attributable to the administration of telmisartan during the period of administration. All AEs should be recorded and, whenever possible, followed until resolution. Documented AEs should contain the following information:

- Severity grade according to CTCAEv4
- Duration: including start and end dates or if the event is ongoing
- Relationship to the study treatment: unrelated, possibly related, related
- Action taken with regard to study treatment
- Whether other medication or therapies were needed and initiated
- Outcome: resolved, not resolved, resolved with sequelae, fatal, or unknown
- Whether it constitutes a serious adverse event (SAE)

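### Section 9.1 excludes transplant-related laboratory abnormalities from adverse events, contradicting its own opening and Section 7.2.1, so mixed-cause grade 3 or greater chemistry abnormalities may never be attributed or reach the intolerance rule

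*Combined protocol and SAP*

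**What the plan says.** All references are to the combined protocol and SAP.

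- **9.1, opening.** The general definition of an AE takes in "laboratory or physiological observations occurring in a study participant, regardless of causal relationship".
- **9.1, second paragraph.** "Laboratory abnormalities associated with subjects underlying disease or related to the subject’s HCT will not be considered adverse events". The exception is a laboratory change "independent from the underlying medical condition and/or HCT that requires medical or surgical intervention, or leads to study drug discontinuation, will be considered an AE". Two conditions must therefore both hold: independence from disease and/or transplant, and either a need for intervention or discontinuation of the drug.
- **7.2.1.** Deviations from baseline are to be noted and assessed for severity and causality. The exclusion that follows is narrower: "Hematologic abnormalities determined to be related to the" subject's disease or transplant are not recorded as AEs. No such exclusion is stated for chemistry.
- **9.2.** "All grade 3, 4, and 5 non-hematologic adverse events will be recorded". Each documented AE is then classed as unrelated, possibly related or related to study treatment.
- **8.4, Telmisartan Intolerance.** The monitored event "includes angioedema and grade 3 or greater drug related adverse events after dose adjustments". The rates behind the boundary are 5% and 11%: "We use 5% as our acceptable rate of intolerance for drug treatment".
- **Named drug risks.** "Hyperkalemia may occur in patients on telmisartan" (5.4.2, and also 1.3.3). Section 1.3.3 describes changes in renal function, including rare acute renal failure. Section 1.3.4 lists abnormal liver function and kidney failure among post-marketing reports, while noting no evidence of a direct link.

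**The concern.** The second paragraph of 9.1 settles attribution before an AE exists. Sections 9.2 and 8.4 act only on AEs. A chemistry abnormality that could be due to the transplant, to telmisartan or to both can therefore be removed upstream, and the *possibly related* category, which exists for such cases, is never reached.

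Overlap of causes is visible in the document itself. Section 5.4.3 says hepatic insufficiency may follow grade III or IV GVHD, and that telmisartan clearance falls in hepatic insufficiency.

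The AE record carries most of the weight here, for four reasons:

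- The safety endpoints in 5.2.2 contain no potassium, renal or hepatic item.
- The monthly reports to the safety board (9.4) are built on AE summary data.
- Section 6.3 has the results of additional standard-care assessments recorded only if they constitute an AE. Between the start of dosing and discharge, the only chemistry panel in the study schedule is at Day +7.
- The trial has no concurrent control arm, so a comparison between groups cannot recover what was not recorded.

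At stake are the secondary objective on safety and tolerability (3.2) and the sensitivity of the intolerance boundary.

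**Working it through.** **Step 1: one case under each passage.** Take a grade 3 potassium, creatinine, bilirubin or transaminase abnormality during dosing whose cause may be the transplant, telmisartan or both.

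| Passage | Is it an AE? |
|---|---|
| 9.1, opening | Yes; cause is irrelevant |
| 9.1, second paragraph | No, if regarded as related to the transplant or not independent of it |
| 7.2.1 | Noted and assessed for causality; not excluded, because it is not hematologic |
| 9.2 | Recorded and attributed, but only if already an AE |
| 8.4, intolerance | Considered, but only if already an AE, grade 3 or greater, drug related, and after dose adjustment |

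The first three rows cannot all be followed. If the second governs, the last two are never reached. This needs no numerical assumption.

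**Step 2: reproduce Table 12.** Inputs are from Table 11 with continuous monitoring. The stopping count b(k) is 2 for patients 1–8, 3 for 9–22, 4 for 23–38, 5 for 39–55 and 6 for 56–60. Let P_k(x) be the probability of being still open after patient k with x events, at event rate p:

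P_k(x) = P_{k−1}(x)·(1 − p) + P_{k−1}(x − 1)·p

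At each k, the mass with x ≥ b(k) is removed as stopped. Crossing sums this over k = 1 to 60. Stopping sums it over k = 1 to 59, that is, before patient 60.

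| p | Crossing (Table 12, high boundary) | Stopping (Table 12) | Expected N (Table 12) |
|---|---|---|---|
| 0.05 | 0.2192 (0.219) | 0.2181 (0.218) | 52.41 (52.4) |
| 0.11 | 0.7978 (0.798) | 0.7943 (0.794) | 30.55 (30.6) |

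Table 12 reproduces. The text's 1% chance of stopping by chance does not match the 5% row; that is a separate matter, and nothing here depends on it.

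**Step 3: illustrate missed events.** If a share f of true intolerance events is never counted, the counted rate is p(1 − f). The documents give no value for f, so 10%, 25% and 50% are assumptions.

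| f | Counted rate at true 11% | Stopping before patient 60 | Expected N |
|---|---|---|---|
| 0 | 0.11 | 0.794 | 30.6 |
| 10% | 0.11 × 0.90 = 0.099 | 0.716 | 34.2 |
| 25% | 0.11 × 0.75 = 0.0825 | 0.566 | 40.3 |
| 50% | 0.11 × 0.50 = 0.055 | 0.269 | 50.7 |

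At f = 50% the rule behaves almost as it does at the acceptable 5% rate (0.218).

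**Step 4: the opposite error.** If background transplant toxicity were counted as drug related and the counted rate rose to an assumed 15% or 20%, the same boundary would stop before patient 60 with probability 0.950 or 0.994. Widening what is recorded and widening what counts toward stopping are therefore separate decisions.

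**The case against.** The strongest reply is that this is a drafting inconsistency with safeguards around it.

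- Section 7.2.1 does have deviations noted and causality-assessed, and the opening of 9.1 disregards cause. **This stands in part.** The information may exist in source records, but neither passage cancels the explicit exclusion that follows in 9.1.
- Section 9.1 is not the only gate. The intolerance rule also requires the event to be drug related and to be counted after dose adjustment, so an abnormality attributed wholly to the transplant would stay out even if 9.1 were rewritten. **This stands.** The loss attributable to 9.1 is confined to mixed or uncertain causes.
- Sections 5.4.2 and 5.4.3 provide for renal, electrolyte and hepatic monitoring, and the safety board may ask for other data (9.4). **This stands as protection for patients.** It does not feed Table 11.
- Section 1.3.4 reports a low overall incidence of drug-related laboratory abnormalities. **This is indirect,** since it comes from the telmisartan safety meta-analysis rather than from transplant recipients, but it cautions against assuming a large loss.

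A reader might also infer that 9.1 and 7.2.1 conflict on every chemistry result, or that almost no potassium, creatinine or bilirubin change after transplant could be called independent of it. The documents support neither. A change judged independent that needs intervention or stops the drug is an AE under 9.1 and is not excluded by 7.2.1. Section 5.4.3 shows that causes can overlap, not that they nearly always do.

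**Conclusion.** The point holds as a contradiction with a consequence, and it should be corrected. Under the second paragraph of 9.1, a grade 3 or greater chemistry abnormality of mixed or uncertain cause may never become an AE. It then cannot be attributed under 9.2, enter the board's AE summary or be considered for the intolerance rule. Clinical diagnoses such as acute renal failure can still qualify under the general definition, because the exclusion is limited to laboratory abnormalities.

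The direction of the effect is clear: tolerability would look better and the boundary would be less sensitive. Its size is not. The fall from 0.794 to between 0.716 and 0.269 rests wholly on the assumed 10% to 50% of missed events and on a true rate of 11%. It should not be read as an estimate of bias in this trial, nor as evidence that telmisartan toxicity would go unseen clinically.

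**What to change.** 1. Reconcile 9.1 with 7.2.1 by limiting the disease or transplant exclusion in 9.1 to hematologic abnormalities.
2. State that every grade 3 or greater chemistry abnormality during telmisartan dosing, including potassium, creatinine, bilirubin and transaminases, is recorded as an AE, with relationship assigned afterwards using the three categories in 9.2.
3. State separately whether *possibly related* counts as drug related for Table 11, and check that choice against the 5% and 11% rates. Step 4 of the working shows why this should not follow automatically from item 2. Section 5.3.4 uses the same term as a trigger for dose adjustment, so the definition must be reconciled across both places.

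Items 1 and 2 are changes of wording and use chemistry panels already scheduled at Day +7 and later study visits. Their cost is more AE entries and a somewhat higher reported toxicity rate. Item 3 may require the boundary rates to be re-justified.
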